- *U.S. Food and Drug Administration Chapter I of Title 21 CFR 50 and 56 (for FDA regulated research only) and related guidance documents.*
- *Commonwealth of Virginia Code of Virginia 32.1 Chapter 5.1 Human Research (for all research).*

IRB PERFORMANCE SURVEY:

We value your feedback! Please take 1-2 minutes to complete the IRB Performance Survey in relation to your experience with this

approved submission: <https://IRBperformancesurvey.questionpro.com>

Managing Cancer and Living Meaningfully (CALM) in Primary Brain Tumor Patients

SIGNIFICANCE

Brain cancer is associated with disproportionate financial impact, symptom burden, and functional impairment. Brain cancer is the third most common cancer diagnosed in young adults and the eighth-most common among those age 40 and older.¹ Estimates place the prevalence rate for PBT in the United States (US) at 0.21% of the population (more than 700,000 affected individuals), with an additional 87,000 individuals diagnosed in 2020 alone.² Brain tumors incur both the highest per-patient initial care cost (mean net cost approaching \$150,000) and the highest per-patient last-year-of-life care cost (mean net cost ranging from \$135,000 to \$210,000) relative to other cancers.³ Further, the symptoms associated with brain cancer are numerous and include fatigue, sleep disturbance, headache, nausea, seizure, cognitive changes, and neurologic symptoms, such as dizziness, difficulty with balance, sensory problems, and numbness/tingling.⁴ Most patients endorse multiple symptoms of at least moderate severity,⁴ and the vast majority require some form of rehabilitation therapy.⁵ Compared to other cancer populations, individuals with brain cancer are less likely to be employed^{6,7} and more likely to be divorced.⁸ Activities of daily living that promote independence, such as self-care, locomotion/mobility, and driving can be affected by the tumor itself, treatment, or both.^{9,10}

Treatment options for individuals with brain cancer are lacking. Despite medical advances that have nearly doubled median survival rates over the past decade,^{11,12} there is still no cure for malignant brain cancer. Glioblastoma multiforme, the most common type of malignant PBT, has a median overall survival rate of 15 months and a five-year survival rate of 6.8%.² It is estimated that over 18,000 people with a malignant PBT will die each year. Furthermore, medical interventions targeting amelioration of PBT are associated with a range of adverse effects, including cognitive decline and fatigue, compounding the symptoms of the disease itself. Given this poor prognosis, medical management often focuses on symptom alleviation (e.g., the provision of steroids to reduce brain swelling, anticonvulsants to reduce seizure frequency).¹³ Tailored, evidence-based psychosocial interventions for individuals with brain cancer have not been available.

Brain cancer is associated with significant distress and reduced quality of life. In the absence of curative medical treatments for malignant PBT, care must include a focus on improving quality of life and reducing psychological burden. Nearly all patients with PBT (93%-95%) report symptoms of depression,^{14,15} with rates of clinical diagnoses greater than both other oncology populations and the general population (22%-41% v. 13% v. 7%, respectively).¹⁵⁻²⁰ Our own preliminary data demonstrate that those with PBT endorse a particular type of distress—death anxiety—at a drastically higher rate than other cancer populations (81% v. 32%).²¹ Death anxiety refers to fear and preoccupation with thoughts of death and dying that may interfere with individuals' daily functioning. Anxiety regarding death is understandable among those with brain cancer given the uncertain disease trajectory, lack of curative treatment, potential loss of functioning, and the inherent existential nature of brain cancer itself.²² Distress of this kind in individuals with advanced cancer has been shown to be ameliorated by psychotherapeutic intervention.²³

Individuals with brain cancer are significantly underrepresented—and often purposely excluded—from behavioral and psychosocial investigations. Despite documented high rates of distress among those with PBT, little is known about the trajectory of this distress, its correlates, or effective treatments. Our research team recently conducted a systematic review of the extent to which individuals with brain cancer are included in psycho-oncology research focused on death-related distress. Results revealed that this patient population represented only 0.18% of participants included in such studies.²⁴ Frequently, this omission is not due to oversight, but rather is purposeful and based on the unsubstantiated assumption that individuals with brain cancer are not cognitively capable of participating in such research. While those individuals with PBT are at risk for cognitive decline, only a small sub-sample demonstrate cognitive impairment to an extent that would exclude them from research studies. In our own research using a common cognitive screener, the Mini Mental State Exam (MMSE), we found that the majority (66%) of patients with PBT passed this eligibility screener, with 25% performing in the range indicative of mild neurocognitive disorder (mNCD) and only 9% performing in the range reflective of dementia.²⁵ In short, the need for inclusion of those with PBT in research is clear, and their exclusion from

behavioral and psychosocial research represents a significant gap in knowledge. The capacity of these individuals to consent and to engage in study tasks is nuanced, highlighting the urgent need for research designed and conducted by investigators familiar with this vulnerable population and its unique challenges and considerations.²⁶

[figure not shown]

Figure 1. Domains of CALM

An effective evidence-based treatment to address psychological distress in advanced cancer exists—but has never been investigated in brain cancer. Though cognitive behavioral therapy (CBT) is effective for a variety of psycho-oncology concerns, it is less effective for individuals with advanced cancer.^{27–29} Indeed, a recent large-scale randomized controlled trial (RCT) found CBT to be ineffective for treating symptoms of depression in patients with advanced cancer.³⁰ Similarly, psychopharmacological approaches are of limited benefit for this population, and are often contraindicated for individuals with PBT. Research further demonstrates that antidepressant use is associated with lowered seizure thresholds, cognitive decline, and worsened fatigue among individuals with PBT;³¹ and, the use of antidepressants has been shown to be an independent predictor of tumor recurrence in this population.³² An

alternative intervention, Managing Cancer and Living Meaningfully (CALM), was designed to specifically address the inevitable challenges patients with advanced cancer face (Figure 1). CALM is a brief, individual, manualized, supportive-expressive psychotherapeutic intervention developed by leaders in psycho-oncology and palliative care.^{23,33,34} CALM research conducted over the past decade has shown CALM to be feasible and acceptable,^{35–37} and a large recent RCT has shown that CALM is effective in treating and preventing depression at 3 and 6 months compared with usual care.²³ Notably, CALM is the only intervention shown to significantly decrease death anxiety.³⁸ No adverse events were reported during the RCT, including increased risk for suicide. However, due to the perceived challenges outlined above, to date, individuals with brain cancer have been excluded from CALM trials.

SPECIFIC AIMS

AIMs: To conduct a mixed-method *Phase IIa Proof-of-Concept Trial* (N = 12) with post-session surveys and individual exit interviews to guide CALM adaptation and determine preliminary feasibility and acceptability in patients with PBT.

Exploratory AIMS.

1. To examine within-group changes in depression, distress about death and dying, and quality of life in order to assess preliminary efficacy in this population.

HYPOTHESES

We hypothesize that it will be feasible to recruit participants into a controlled trial, to evaluate and follow study participants and to preliminarily assess the efficacy of CALM in individuals with brain cancer. Preliminary information on CALM feasibility will be collected with regards to the ability to consent patients to the study, study session attendance, post-session assessment and follow-up assessment completion, and participant satisfaction ratings.

RESEARCH STRATEGY AND FEASIBILITY

Approach. A mixed-methods approach, utilizing the NIH Science of Behavior Change (SOBC) supported ORBIT model^{43,44} has been chosen for this study. The ORBIT model begins with a theory grounded in behavioral science about the mechanisms of behavior change (Phase I), and develops an intervention in small incremental steps, paying attention to tailoring, acceptability, and testing efficacy of early outcomes using smaller experiments (Phase II), before embarking on a randomized controlled trial (Phase III).

Study Population. Diagnosis and classification of brain cancer will be based on 2016 World Health Organization

revised criteria.⁴⁵ At VCU, 160 individuals with PBT are treated annually. For individuals with PBT, most are White (76%) followed by African American (16%) and most are men (59%). The majority fall into the younger age range (59%; 18-54 years).

Inclusion Criteria. This study will consider for enrollment individuals of all genders, ethnic, racial, and socioeconomic backgrounds. PBT participants must: (1) have a confirmed malignant brain cancer diagnosis via histopathology, (2) be a minimum of 2 weeks post-surgical resection or biopsy (if applicable), (3) be primarily English speaking, (4) be age 18+, (5) obtain ≥ 20 on Telephone Interview for Cognitive Status, (6) have current elevated depression (Patient Health Questionnaire-9 Item [PHQ9] ≥ 10) or death anxiety symptoms (Death and Dying Distress Scale [DADDS] ≥ 15),²³ and (6) have reliable internet connection.

Exclusion Criteria. This study will exclude participants with: (1) Major communication difficulties as determined by the research team which would prohibit psychotherapeutic interaction, (2) inability to meet with interventionist via an electronic device for telehealth intervention sessions, or (3) inability to provide informed consent.

VCU Recruitment. VCUHealth treats approximately 160 individuals with PBT annually. Participants will be directly referred by their neuro-oncology clinical team. Flyers will also be posted in treatment rooms. If patients are interested in participating, a telehealth screening interview will be scheduled. Trained study staff will screen for eligibility. If eligible, individuals will have the study described to them. Interested individuals will be emailed and asked to read the consent form and encouraged to ask any questions. They will be informed that their decision to (or not) participate will not affect their care at any VCU facility. Once all questions are answered, interested individuals will be asked to sign the consent form electronically. We anticipate participation rates similar to those reported in prior advanced cancer behavioral health and psychotherapeutic trials, with $\geq 70\%$ consenting to screening and $\geq 30\%$ of eligible patients enrolling (**Table 1**).^{23,35,36,40,41}

Scientific Rigor. To parallel the multi-phase drug development scientific process, including intervention development and dose-response testing (Phase I), feasibility and acceptability evaluations (Phase II), and eventual Phase III efficacy trials, the NIH SOBC ORBIT model was selected to guide this project (**Figure 5**).⁴³ To promote a robust and unbiased approach, we will: (1) use validated measures (**Table 2**), (2) have a non-clinical research assistant (RA) conduct eligibility screening and consent to reduce coercion, and (3) have the RA collect participant measures and conduct exit interviews.

AIM 1: Proof-of-Concept Trial Design. Using the ORBIT model, we will initially conduct a 1-year Phase IIa *Proof-of-Concept Trial* (N=12) to guide CALM implementation for individuals with PBT. Within one week before and after the intervention and 3 months post-intervention (if applicable given terminal illness; **Figure 6**), participants will be asked to complete self-report surveys of behavioral and psychological variables (**Table 2**) via a secure online data collection system (REDCap). Participants will be offered a \$20 gift card for completing these surveys across each of the 3 timepoints (pre-intervention, post-intervention, follow-up). If paper copies of the questionnaire are preferred by the participant, these can be mailed and the RA will input any data into REDCap upon return. Six sessions of CALM therapy will be provided at no cost to participants. After each intervention session, participants will be sent a link for a brief post-session satisfaction survey via secure email link. Participants will rate 1) topic applicability; 2) perceived benefit of session; 3) comfort with interventionist(s); and 4) overall satisfaction. Participants who withdraw will be contacted and asked open-ended questions on reasons for termination and suggestions for improvement. Interventionists will also complete surveys at the end of each session which address: 1) topic applicability; 2) perceived participant response; 3) suggestions for improvement.

Within one month of intervention completion, the RA will conduct individual exit interviews by phone (**Figure 8**), which will be audio recorded for verbatim transcription. Interviews will assess length and number of sessions, content applicability, recommended modifications, helpful and unhelpful aspects of sessions, perceived benefits, overall satisfaction, and suggestions for improvement. This will inform treatment preferences, intervention adaptations, and overall satisfaction. Our team has used these survey and interview measures with success in prior

treatment development trials.^{49,50} At any time during the intervention, participants considered by the therapist to be at acute risk for suicide, or who demonstrate significant worsening of depression or other psychiatric comorbidities that require treatment, will be referred for psychiatric assessment and treatment in the Department of Psychiatry. This may include pharmacotherapy or other psychiatric interventions.

[figure not shown]

Figure 6. AIM 1 Intervention Timeline

CALM Interventionists. The PI has attended four international CALM advanced training workshops (2018: Toronto; 2019: London and Banff; 2020: Virginia). The PI is CALM certified and receives ongoing supervision from CALM founder on a bi-weekly basis to discuss cases, therapeutic fidelity, supervision of interventionists, and research procedures. The PI will supervise implementation of the CALM intervention by psychology post-doctoral and doctoral trainees. All interventionists will also have attended at least one 3-day CALM training workshop and participate in ongoing weekly supervision.

Assessment Measures.

Covariates. Baseline self-report data will include: age, gender, ethnicity, race, educational status, employment, marital and parental status, history of substance abuse and/or mental health history (psychiatric diagnoses, suicidal ideation), and self-reported social support and spirituality beliefs. We will extract the following data from medical records: time since diagnosis, tumor characteristics and treatment, seizure history, and psychopharmacological medication history. Patients' oncologists will report on estimated prognosis. Additional psychological intervention (e.g., psychotherapy, pastoral care, social work) and/or psychopharmacological medication use will also be tracked throughout the intervention and follow-up time period.

Table 1. Primary Outcomes

Feasibility*	
Recruitment	$\geq 70\%$ consent to screening; $\geq 30\%$ of eligible enroll
Eligibility	Reasons for ineligibility, reasons for refusal, characteristics for refusers
CALM intervention	$\geq 60\%$ session attendance; $\geq 70\%$ post-session assessments completed; $\geq 60\%$ follow-up assessments completed
Acceptability*	
CALM intervention	Session ratings of: satisfaction, helpfulness, enjoyment, relevance, utility (Likert Scale; 1=not at all, 5=very much; M ≥ 4 post-session surveys); overall program satisfaction (M ≥ 4); $\geq 75\%$ would recommend program to others (post-intervention survey); likes, dislikes, adaptations, future suggestions (exit interview)

Note. M = mean; *based on CALM trial data^{23,35,36} and additional intervention studies of patients with advanced disease⁴⁰⁻⁴²

Table 2. *Exploratory Outcomes*

Variable	Measurement	Minutes to Complete
Depression	Patient Health Questionnaire – 9 Item (PHQ9) ^{33*}	2 – 5
Generalized Anxiety	Generalized Anxiety Disorder – 7 Item (GAD7) ^{34*}	2 – 5
Death Distress	The Death and Dying Distress Scale (DADDS) ^{35*}	5 – 10
Fear of Cancer Recurrence	Fear of Cancer Recurrence - 7 Item (FCR7) ³⁶	2 – 5
Attachment	Experiences in Close Relationships Inventory (ECR-M-16) ^{37*}	5 – 10
Quality of Life	Quality of Life at the End of Life-Cancer Scale (QUAL-EC) ^{38*}	5 – 10
Suicidal Ideation	Patient Health Questionnaire – Item 9 (PHQ9) ^{33*}	--
Clinical Evaluation	Clinical Evaluation Questionnaire (CEQ) ^{39*}	2 – 5

Note. *Measures used in the CALMRCT

DATA ANALYSIS.

Primary Outcomes. Detailed records of the number of individuals who screen, are eligible, enroll, complete assessment measures, and attend telehealth sessions will be kept. Reasons for attrition will be recorded. Individuals who “no-show” will be contacted to assess continued interest and will be rescheduled as appropriate. Each attempt to contact participants will be recorded. This information will guide future recruitment/retention and inform feasibility. Recruitment source will be tracked to determine the most fruitful strategies. We will calculate frequencies and proportions to explore preliminary feasibility outcomes and means and standard deviations or medians and interquartile ranges to assess preliminary acceptability (**Table 1**). The two-sample t-tests and/or Mann-Whitney U-test, and chi-square tests will be used to compare eligible patients who did and did not enroll in terms of demographic, medical, and psychiatric variables.

Exploratory Outcomes. Within-group changes in behavioral and psychological variables will be explored to prepare for future pilot and efficacy trials. Thus, for each data collection time points we will calculate the mean and standard deviation of exploratory outcomes. In addition, we will calculate the correlation on the measures between time points as well as calculating the difference scores and the accompanying standard deviations.

POTENTIAL CHALLENGES AND SOLUTIONS

Our previous track record of research accomplishments clearly demonstrates our capacity to conduct the proposed research. The proposed qualitative methods will ensure that intervention components are appropriately adapted and aligned with patient preferences and capabilities. If enrollment is less than expected, recruitment will be expanded to greater Richmond community hospitals with which the PI has a long-standing collaborative relationship with. If eligibility rates are less than expected, we will consider enrolling individuals with high-risk grade II PBT. If intervention adherence is low, we will aim to align appointments with neuro-oncology clinic days and provide the option for in-person CALM sessions for those unable or unwilling to participate in an online intervention. Attrition due to disease progression is a concern. If necessary, additional participants will be recruited. All visits are being scheduled and completed using a telehealth format as to negate in-person safety issues with COVID-19. If telehealth is not an option for an individual, we can consider in-person clinic visits following all Centers for Disease Control and Prevention guidelines.

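### The only suicide-risk referral rule covers the intervention period, yet PHQ-9 item 9 is asked twice after the last session with no required review or referral

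*Combined protocol and SAP*

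**What the plan says.** The referral rule is one sentence in the section on the AIM 1 Proof-of-Concept Trial Design. It opens "At any time during the intervention, participants considered by the therapist to be at acute risk for suicide", adds participants whose depression or other psychiatric condition deteriorates enough to need treatment, and states that they "will be referred for psychiatric assessment and treatment in the Department of Psychiatry". The opening time phrase governs both parts. No score threshold is given for either.

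The same section schedules the Table 2 surveys "Within one week before and after the intervention and 3 months post-intervention (if applicable given terminal illness" applies at the last time point). They are self-completed in REDCap, or on paper, in which case "these can be mailed and the RA will input any data into REDCap upon return". Table 2 lists suicidal ideation as an outcome in its own right, measured by "Patient Health Questionnaire – Item 9 (PHQ9"), alongside the full PHQ-9.

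Two other contacts fall to staff after sessions end. "Within one month of intervention completion, the RA will conduct individual exit interviews by phone", and participants who withdraw are asked why they stopped and what could be improved.

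The Scientific Rigor paragraph says the team will "have a non-clinical research assistant (RA) conduct eligibility screening and consent to reduce coercion", and then gives the RA the collection of measures and the exit interviews. Under Data Analysis, Exploratory Outcomes, "for each data collection time points we will calculate the mean and standard deviation of exploratory outcomes", together with correlations between time points and difference scores.

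**The concern.** The plan asks about suicidal thoughts at two points after the last session, and its written safety rule does not reach them. For suicide risk, the rule depends on a therapist's judgment, and no scheduled contact with the therapist remains by then.

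The stake is patient safety, not inference. Entry requires a malignant brain cancer and either PHQ-9 of at least 10 or DADDS of at least 15 (Inclusion Criteria). The Significance section cites clinical depression in 22% to 41% of patients with primary brain tumors. Under Potential Challenges and Solutions, the sponsor names disease progression as a cause of attrition. A participant could report suicidal thoughts at 3 months, and staff could follow the protocol to the letter without anyone having to read that answer as an individual response.

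**Working it through.** No power or error-rate calculation applies. The check sets each contact against the window of the rule, then counts the surveys that fall outside it.

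**Contacts against the rule**

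| Contact | Timing | Asks about suicidal thoughts? | Inside the window? |
|---|---|---|---|
| Pre-intervention survey | within a week before | Yes, item 9 | No, but sessions follow within about a week |
| Six CALM sessions | intervention | Therapist judges risk | Yes |
| Post-intervention survey | within a week after | Yes, item 9 | No |
| Exit call by the RA | within a month of completion | No, program feedback | No |
| 3-month survey | 3 months after, if applicable | Yes, item 9 | No |
| Contact after withdrawal | not stated | No, reasons and suggestions | No; that person's sessions have stopped |

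**Does intervention mean the whole study?** The AIM 1 section dates the last survey and the exit call relative to the end of the intervention. The Covariates paragraph names intervention and follow-up as two periods when it says other treatment will be tracked through both. The natural reading is that the rule ends with the last session.

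**Is there another rule elsewhere?** Suicide appears in three other places: as a finding of the earlier CALM randomized trial (Significance), as baseline history (Covariates) and as the Table 2 outcome. None of these is an instruction to act. Tracking other psychological care through follow-up records treatment and triggers none. The analysis text uses the post-treatment scores only as summaries.

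**Which contacts carry the point?** The two post-treatment surveys, because they put the question. The exit call and the withdrawal contact are secondary: a disclosure could occur in either, but neither is designed to elicit one. The pre-intervention survey is a minor gap because therapist contact follows soon after.

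**Exposure**

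- Post-treatment item-9 surveys per participant: 1 (within a week after) + 1 (3 months) = at most 2.
- At the planned N=12: 2 × 12 = 24.
- If k additional participants are recruited, as Potential Challenges and Solutions permits: 2 × (12 + k), so 24 is the maximum for the planned sample only.

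**The case against.** The strongest objection is that the public text is incomplete. It accompanied an approved IRB submission; the consent pages and Figures 6 and 8 are not shown, and Figure 8 is the one cited for the exit interview. A distress procedure could sit there. This stands, and it is why the first step is to confirm. A reader might infer that the trial has no safety procedure after treatment. The documents do not support that: they show only that the available text states none.

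Second, the word intervention is sometimes used loosely. Figure 6, cited for a schedule that includes the 3-month survey, is captioned as an intervention timeline, and the referral sentence comes directly after the exit-interview text. This adds some ambiguity, but the separate naming of follow-up and post-intervention periods makes the narrower reading the more natural one. A safety rule should not rest on the choice.

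Third, non-clinical may mean independent of the care team rather than untrained in risk; the phrase appears beside the aim of reducing coercion. The documents also do not say who can see REDCap answers. It would therefore go too far to say that every positive answer lands with someone unable to respond. What remains is that no role is assigned the task of looking.

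Fourth, participants come from a treating neuro-oncology team, and the earlier CALM trial reported no adverse events. Nothing in the text sends survey answers back to that team. The Significance section also says that brain cancer patients were excluded from CALM trials, so that record does not cover this population.

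**Conclusion.** The point holds for the available text. One referral rule exists, it is limited to the intervention, and PHQ-9 item 9 is asked up to twice per participant afterward with no required review or referral. That is up to 24 surveys at N=12, and more if participants are added. The count measures opportunities for an unreviewed answer, not expected events.

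Three stronger readings should be set aside:

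- A reader might take the Table 1 target of at least 60% follow-up completion as a floor on the number of surveys. It is a target that may be missed, and the 3-month survey is conditional on the course of illness, so no lower bound follows. No item-9 positive rate is given, so the number of participants affected cannot be estimated.
- A reader might infer that PHQ-9 answers are never used individually. They are, for eligibility (Inclusion Criteria). The statement about group-level use applies only to post-treatment scores.
- A reader might treat the exit call as a missed risk assessment. Its listed topics are program feedback.

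The conclusion assumes that intervention in the referral sentence means the treatment period, and that no unseen approved procedure covers the later contacts. It is a cheap improvement that should be confirmed or made.

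**What to change.** First check whether an IRB-approved procedure already covers the post-treatment contacts. If so, cite it next to the referral sentence and change nothing else.

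If not, make two changes in the AIM 1 section:

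1. Replace the opening time phrase of the referral sentence with: *At any time from the pre-intervention survey through the 3-month follow-up, including after withdrawal*.
2. Add that the RA promptly alerts the PI or another existing study clinician to a positive item-9 answer, a PHQ-9 worsening, or a disclosure of suicidal thoughts in any RA contact. The PI sets the thresholds and response time before first enrollment. The alerted clinician decides on the Department of Psychiatry referral already in the plan.

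The documents give no basis for a particular item-9 cutoff, PHQ-9 change or number of hours, so these are left to the PI. Online answers can arrive at any hour, so the response time should be one that existing staff can meet.

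The cost is some RA and clinician time to check incoming surveys, some alerts that prove not to be acute, and possibly one line in the consent form saying that answers may be shared with a study clinician. No new staff, visit or instrument is needed. Screening before consent is left as it is.

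### The primary feasibility and acceptability proportions are compared with numerical marks but reported without any measure of precision, although several rest on 12 people or fewer

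*Combined protocol and SAP*

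**What the plan says.** The design section (AIM 1) describes a "1-year Phase IIa *Proof-of-Concept Trial* (N=12) to guide CALM implementation for individuals with PBT". It gives no precision or error-rate basis for that number. The hypothesis is worded as a feasibility claim: "We hypothesize that it will be feasible to recruit participants into a controlled trial", and to evaluate and follow them.

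Table 1 (Primary Outcomes) attaches a minimum percentage to six proportions:

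- consent to screening, 70%
- enrolment among the eligible, 30%
- session attendance, 60%
- post-session assessments, 70%
- "follow-up assessments completed", 60%
- willingness to recommend the programme, 75%

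Under DATA ANALYSIS, Primary Outcomes, the stated method for feasibility is "We will calculate frequencies and proportions to explore preliminary feasibility outcomes". Acceptability ratings get means with standard deviations, or medians with interquartile ranges. No confidence interval is planned for any proportion. The plan does not say whether attendance and assessment completion are counted per person or per session, nor how a met or missed mark will be used.

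On denominators, the design section states "Six sessions of CALM therapy will be provided at no cost to participants", which gives up to 72 sessions. The 3-month assessment is conditional on the patient's illness. The section on potential challenges expects attrition and allows further recruitment.

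**The concern.** A minimum percentage on a primary outcome, tied to a feasibility hypothesis, invites a met or not-met reading. With a dozen people, one participant moves a proportion by 1/12 = 8.3 percentage points, and a bare percentage hides this. The analysis section says the records will inform feasibility and guide later recruitment and retention. A reader of the results could therefore take a one-person difference as evidence for or against a next trial. The planned output contains nothing to warn against that.

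**Working it through.** **Inputs.** N = 12 and six sessions each (AIM 1 design section); marks from Table 1. The plan gives no power, alpha or precision target, so there is no figure of its own to reproduce.

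**Person-level 60% mark, n = 12.** The count needed is the smallest whole number at or above 0.60 × 12 = 7.2, so 8 (7/12 = 58.3%; 8/12 = 66.7%). The chance of reaching it is P(X ≥ 8) with X binomial(12, p):

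- true 50%: 19.4%
- true 60%: 43.8%
- true 70%: 72.4%, so 27.6% fall short

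**Person-level 75% mark, n = 12.** The count needed is 9. A true 60% reaches it 22.5% of the time and a true 75% reaches it 64.9% of the time.

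**If attrition shrinks the denominator** (60% mark; the documents give no attrition figure, so n = 8 to 12 is an assumed range):

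| n | count needed | reached at true 50% | reached at true 60% |
|---|---|---|---|
| 8 | 5 | 36.3% | 59.4% |
| 9 | 6 | 25.4% | 48.3% |
| 10 | 6 | 37.7% | 63.3% |
| 11 | 7 | 27.4% | 53.3% |
| 12 | 8 | 19.4% | 43.8% |

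**Exact (Clopper-Pearson) 95% intervals.** The lower limit is the 2.5% point of Beta(x, n − x + 1); the upper limit is the 97.5% point of Beta(x + 1, n − x).

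- 7/12: 27.7% to 84.8%
- 8/12: 34.9% to 90.1%
- 9/12: 42.8% to 94.5%

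**Enrolment mark.** Twelve enrolled at 30% implies 12/0.30 = 40 eligible. The interval for 12/40 is 16.6% to 46.5%. With 40 eligible, 12 or more enrol 55.9% of the time at a true 30% and 8.8% of the time at a true 20%.

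**Session attendance counted over sessions.** The count needed is 0.60 × 72 = 43.2, so 44. The documents give no within-person correlation. Assumed values, with beta-binomial simulation for those between 0 and 1, give:

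| correlation | reached at true 50% | reached at true 60% |
|---|---|---|
| 0 | 3.8% | 47% |
| 0.2 | 10.6% | 49% |
| 0.5 | 17.4% | 49% |
| 0.8 | 21.6% | 49% |
| 1 | 19.4% | 44% |

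**Effect on the interval, illustrative pattern only.** Suppose the 12 people attend 6, 6, 6, 6, 6, 5, 4, 2, 1, 1, 1 and 0 sessions, a total of 44 (44/72 = 61.1%). An exact interval that treats the 72 sessions as independent is 48.9% to 72.4%. A t interval on the 12 personal proportions (mean 0.611, SD 0.410, standard error 0.410/√12 = 0.118, t with 11 df = 2.201) is 35% to 87%. This pattern is strongly clustered by construction; a milder one would widen the interval less.

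**The case against.** The strongest reply is that this is a small proof-of-concept study whose text calls the work exploratory and preliminary, and that it sets no pass/fail or go/no-go rule. A reader might infer that 8/12 will be declared feasible and 7/12 not feasible; no sentence says so. Adaptation of CALM also draws on exit interviews, session surveys and reasons for refusal and withdrawal, so the percentages do not stand alone. All of this is right, and it limits the point to how the proportions are reported.

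Three further inferences would go too far:

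- **That every mark rests on 12 people.** Recruitment marks use people approached or eligible, and attendance and post-session completion may be counted over up to 72 sessions.
- **That a programme truly at 60% tends to fail its own mark.** This holds at n = 12 and n = 9 but reverses at n = 8, 10 and 11. Any estimate whose true value sits on the threshold passes about half the time at any sample size. The chances at a true 50% and 70% are more informative.
- **That sessions will be lost in blocks.** The plan says no-shows are contacted and rescheduled, and it gives no attendance pattern.

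It can also be said that readers could compute intervals from reported counts. For person-level rates they could, if numerators and denominators are published. For session-based rates they could not without each participant's data. The omission of any precision measure therefore stands.

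**Conclusion.** The point holds as a gap in the reporting of the primary proportions. For a per-person 60% mark with 12 in the denominator, a true rate 10 points below the mark reaches it about one time in five, and a true rate 10 points above misses it more than one time in four. Neighbouring results on either side of the mark have nearly the same interval. These figures assume that each person counts once, that all 12 are included and that participants are independent; follow-up completion and willingness to recommend fit best. The recruitment marks are less affected but still imprecise. For session-based rates the direction is clear if attendance is positively correlated within person (a session-level interval is too narrow), but the size depends on an assumed pattern.

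A reader might infer that the study is too small or needs a formal test. The documents do not support that: they claim only preliminary feasibility, which 12 people can inform if the uncertainty is shown.

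**What to change.** Amend DATA ANALYSIS, Primary Outcomes, along these lines:

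*Each person-level proportion in Table 1 will be reported with its numerator, denominator and exact 95% confidence interval. Session attendance and post-session completion will be summarised as a proportion per participant, with a 95% interval computed over participants, not over sessions. Each mark will be interpreted alongside its interval, and feasibility will not be claimed from the point estimate alone.*

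Table 1 should state the unit and denominator for each mark, including who counts at follow-up when the 3-month assessment does not apply.

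The intervals should be used descriptively. A rule that labels each mark met, not met or not distinguishable according to whether the interval excludes it should not be adopted. At n = 12 the 75% mark could never be met, since 12/12 has a lower limit of 0.025^(1/12) = 73.5%. The 60% mark would be met only at 11 or 12 of 12, which a programme truly at 80% achieves 12 × 0.8^11 × 0.2 + 0.8^12 = 27% of the time.

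The cost is a few sentences and a few lines of code. The intervals will be wide and the conclusions more cautious. Sample size, conduct and participant burden do not change.
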